4 STUDY ENDPOINTS

4.1 PRIMARY EFFICACY ENDPOINT

There are 2 separate primary endpoints which are defined for US (FDA) submission and Ex-US submission respectively.

US (FDA) submission.

The primary efficacy endpoint for the US submission is the Mean Hb change from baseline (using central laboratory values) to the average level during the Evaluation Period, defined as Week 28 until Week 52. This analysis will be based on the intent-to-treat (ITT) population. Hemoglobin values under the influence of rescue therapy (see definition below) will not be censored for the primary analysis.

Ex-US submission

The primary efficacy endpoint for the Ex-US submission is defined as the proportion of subjects who achieve a Hb response at two consecutive visits at least 5 days apart during the first 24 weeks of treatment, without rescue therapy (see definition below) within 6 weeks prior to the Hb response in the Per Protocol Set (PPS). A Hb response is defined, using central laboratory values, as:

- Hb ≥ 11.0 g/dL and a Hb increase from baseline by ≥ 1.0 g/dL in subjects whose baseline Hb > 8.0 g/dL, or
- Increase in Hb ≥ 2.0 g/dL in subjects whose baseline Hb ≤ 8.0 g/dL.

Rescue therapy for roxadustat treated subjects is defined as recombinant erythropoietin or analogue (ESA) or RBC transfusion, and rescue therapy for Epoetin alfa treated subjects is defined as RBC transfusion. All endpoints using Hb are based on the central lab data.

Baseline Hb is defined as the mean of at least the last 3 available central laboratory Hb values prior to first dose of study medication: three last screening Hb values plus the pre-dose Hb value collected on day 1. In subjects with missing Day 1 Hb value, the mean of three last screening laboratory Hb values will be considered as baseline Hb value.

Hb values from the central laboratory will be sorted by visit date. If two consecutive on-treatment Hb values from the central laboratory meet the Hb response criteria defined by primary efficacy endpoint for the Ex-US submission, the subject will qualify for Hb response as long as there is no rescue therapy 6 weeks before the date of the first of these 2 Hb measurements.

The classification of Hb response shall take into account all consecutive Hb values regardless of whether they are obtained at scheduled or unscheduled visits.

RBC transfusion is collected in the Blood Transfusions form of the eCRF. The use of ESA is recorded in the related forms of the eCRF and coded into ATC (Code: B03XA01) and generic name.

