### 6.1.2.3 Weeks 6 to 24 (Every 2 weeks, $\pm 4$ days)

- Laboratory tests (must be performed prior to dosing):
  - Weeks 8, 12, 20: CBC with WBC differential
  - Week 6 followed by every visit where no CBC is collected; Hb only.
  - Weeks 8, 12, 20: Serum chemistry
  - Weeks 6, 16: LFTs and CPK
  - Weeks 8, 12, 24: Lipid panel (fasting whenever possible).
  - Weeks 8, 12, 20: Serum iron, ferritin, TIBC, TSAT.
  - Weeks 8, 12, 20: CHr
  - Week 12: HbA1c
  - Weeks 8, 20: Reticulocyte count
  - Weeks 12, 20: Special laboratory analytes

- Weeks 12, 20: Archival serum/plasma samples (optional donation, separate consent form)
- HemoCue®/CritLine® assessment
- Weeks 12, 24: Serum hCG pregnancy test for women of childbearing potential (for definition, see [Section 3.6.6](#))
- 
- Week 24 followed by every 12 weeks: Targeted physical exam (eg, respiratory and cardiovascular system)
- Week 24 followed by every 24 weeks: 12-lead ECG, weight (HD subjects: dry weight)
- Dose adjustment review every 4 weeks (except in the event of excessive hematopoiesis or dose frequency conversion). Refer to [Section 3.5.2](#), and [Appendix 2](#).
- All visit weeks: BP and HR
- Week 12 HRQoL questionnaires (SF-36, FACT-An, and EQ-5D-5L)
- Adverse event recording
- Concomitant medication recording
- Procedures and nondrug therapy recording
- Dispense study drug

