### 7.1 Primary Endpoint:

- **US (FDA) submission:** Mean Hb change from baseline to the average level during the Evaluation Period, defined as Week 28 until Week 52. This analysis will be based on the intent-to-treat (ITT) population. Hemoglobin values under the influence of rescue therapy will not be censored for the primary analysis.
- **Ex-US submission:** The proportion of subjects who achieve a Hb response at two consecutive visits during the first 24 weeks of treatment, without rescue therapy within 6 weeks prior to the Hb response. This analysis is based on the Per Protocol Set (PPS) population.

A Hb response is defined, using central laboratory values, as

- Hb  $\geq 11.0$  g/dL and a Hb increase from baseline by  $\geq 1.0$  g/dL in subjects whose baseline Hb  $> 8.0$  g/dL, or
- Increase in Hb  $\geq 2.0$  g/dL in subjects whose baseline Hb  $\leq 8.0$  g/dL

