### 7.2 Secondary Endpoints

- **US (FDA) submission:** The proportion of subjects who achieve a Hb response at two consecutive visits during the first 24 weeks of treatment, without rescue therapy within 6 weeks prior to the Hb response.

A Hb response is defined, using central laboratory values, as

- Hb  $\geq 11.0$  g/dL and a Hb increase from baseline by  $\geq 1.0$  g/dL in subjects whose baseline Hb  $> 8.0$  g/dL, or
- Increase in Hb  $\geq 2.0$  g/dL in subjects whose baseline Hb  $\leq 8.0$  g/dL

- **Ex-US submission:** Mean Hb change from baseline to the average level during the Evaluation Period, defined as Week 28 until Week 36 without rescue therapy within 6 weeks prior to and during the evaluation period. This analysis will be based on the PPS population.

Both, US and ex-US Submissions:

- Average monthly IV iron use per subject during the Treatment Period. Mean change in low-density lipoprotein (LDL) cholesterol averaged over Weeks 12 to 24.

- Blood pressure effects:
  - Proportion of subjects with exacerbation of hypertension, meeting at least one of the following criteria:
    - Increase in BP: An increase from baseline of  $\geq 20$  mm Hg systolic BP and sBP  $>170$  mmHg, or an increase from baseline of  $\geq 15$  mm Hg diastolic BP and dBP $>100$  mmHg. Increases from baseline in blood pressure must be confirmed by repeat measurement.
  - Time to an increase in BP as defined above.
  - Mean change in mean arterial pressure (MAP) averaged over Weeks 8 to 12.
- Time to achieve first Hb response as defined by the primary endpoint (ex-US) (which is the secondary endpoint for the US [FDA]).

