The analysis will be repeated with Hb values under the influence of rescue therapy censored. Namely, set Hb to missing for Rescue Medication and 6 weeks afterwards (or 8 weeks if during the evaluation period).

Ex-US Submission: The primary efficacy endpoint for Ex-US submission is defined as the proportion of subjects who achieve an Hb response at two consecutive visits during the first 24 weeks of treatment, without rescue therapy within 6 weeks prior to the Hb response.

- A Hb response is defined, using central laboratory values, as: $Hb \geq 11.0$ g/dL and a Hb increase from baseline by ≥ 1.0 g/dL in subjects whose baseline $Hb > 8.0$ g/dL, or
- Increase in $Hb \geq 2.0$ g/dL in subjects whose baseline $Hb \leq 8.0$ g/dL

Rescue therapy for roxadustat treated subjects is defined as ESA rescue or RBC transfusion, and rescue therapy for epoetin alfa treated subjects is defined as RBC transfusion.

The hypothesis to be tested for the primary efficacy analysis is:

H_0 : Hb response rate for subjects in the roxadustat arm - Hb response rate for subjects in the epoetin alfa arm $\leq -15\%$

Versus

H_1 : Hb response rate for subjects in the roxadustat arm - Hb response rate for subjects in the epoetin alfa arm $> -15\%$

A two-sided 95% CI for the difference of 2 responder rates (roxadustat minus epoetin alfa) based on the Miettinen & Nurminen approach adjusting for treatment and stratification factors will be calculated and this null hypothesis will be rejected if the lower bound of the 95% CI is greater than -15%. Subjects who dropped out from the study without data for the assessment will be treated as non-responder.

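### The SAP responder rule does not check for rescue between the two qualifying Hb values, so a confirming value obtained after rescue can count towards a response without rescue

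*SAP*

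**What the plan says.** Protocol section 7.1 defines the ex-US primary endpoint as an Hb response at two consecutive visits in the first 24 weeks, "without rescue therapy within 6 weeks prior to the Hb response. This analysis is based on the Per Protocol Set (PPS) population". SAP section 11.1.2 has nearly identical text: "proportion of subjects who achieve an Hb response at two consecutive visits during the first 24 weeks of treatment, without rescue therapy within 6 weeks", counted back from the response. Neither text says which of the two visits dates the response.

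SAP section 4.1 states the endpoint as an "Hb response at two consecutive visits at least 5 days apart during the first 24 weeks of treatment" and then gives the working rule. Two consecutive on-treatment central values that meet the criteria make the subject a responder "as long as there is no rescue therapy 6 weeks before the date of the first of these 2 Hb measurements". Classification "shall take into account all consecutive Hb values regardless of whether they are obtained at scheduled or unscheduled visits".

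Rescue differs by arm. In SAP 4.1, "Rescue therapy for roxadustat treated subjects is defined as recombinant erythropoietin or analogue (ESA) or RBC transfusion"; in the epoetin alfa arm only RBC transfusion counts.

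For the Week 28 to 36 mean-change endpoint, Protocol section 7.2 (and SAP section 4.3) asks for Hb "without rescue therapy within 6 weeks prior to and during the evaluation period". In the rescue-censored repeat of the US primary analysis, SAP 11.1.2 sets Hb to missing for rescue and the 6 weeks after it (8 weeks if during the evaluation period).

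**The concern.** The second value is there to confirm the first. If rescue falls between them, the confirmation may come from the rescue and not from study drug, yet the rule still records an unrescued response.

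The rule is also inconsistent with itself. A value taken one week after a transfusion cannot be the first of a qualifying pair, because the 6-week look-back catches the transfusion. The same value is accepted as the second of a pair.

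Three endpoints use this definition: the ex-US primary (SAP 4.1, 11.1.2), the US first secondary (SAP 4.3, 11.2.1.1) and time to first Hb response (SAP 11.3.1.1). The alternative definition in SAP 4.2.1 drops the rescue condition altogether. Affected subjects are responders under both definitions, so comparing the two does not show them.

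**Working it through.** **1. Does any other text close the gap?**

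| Place | Rescue handling | Covers the interval between the two values? |
|---|---|---|
| Protocol 7.1; SAP 11.1.2 | within 6 weeks before the response | Only if the response is dated at the second visit; not stated |
| SAP 4.1, derivation | 6 weeks before the first value | No |
| SAP 4.2.1, sensitivity | ignored | No |
| SAP 4.3, Week 28–36 mean Hb | before and during the period | Yes, for that endpoint |
| SAP 11.1.2, censored US analysis | missing at rescue and for 6 weeks after | Yes, for that analysis |

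The derivation in SAP 4.1 is the only text that fixes the anchor, and it fixes it at the first value.

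**2. Length of the unchecked interval.** Protocol 6.1.2.3 schedules visits every 2 weeks from Week 6 to Week 24, ±4 days. Nominal gap: 14 days. Largest gap with both visits in window: 14 + 4 + 4 = 22 days. (SAP Appendix 1 still shows ±2 days, giving 14 + 2 + 2 = 18.) A missed visit lengthens it, and no maximum is set.

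**3. Example.** Take baseline Hb 9.0 g/dL, Hb 11.1 at Week 10, a transfusion at Week 11 and Hb 11.2 at Week 12, with no central value in between. The rule looks back 6 weeks from Week 10, finds no rescue and records a responder. With the interval checked, the Week 10/12 pair fails. The subject could still qualify later: the look-back clears after Week 17, so the scheduled pairs 18/20, 20/22 and 22/24 remain. Responder status might then be unchanged, although the response date would move. The last scheduled pair starts at Week 22, so rescue after Week 22 − 6 = Week 16 leaves no later clean scheduled pair.

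**4. The plan's own figure.** SAP 5.1 gives at least 99% power for 80% v 80%, margin −15%, at least 600 subjects, 1:1. With a normal approximation, unpooled variance and one-sided 0.025:

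Power = Φ(0.15/√(2 × 0.80 × 0.20/300) − 1.96) = 99.58%.

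The stated power reproduces. This is not the stratified Miettinen–Nurminen interval of the analysis, but it is adequate for illustration.

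**5. Sensitivity to an assumed frequency.** The documents give no rate. Let x be the share of roxadustat responders who lose responder status when the interval is checked, with none in the epoetin arm. This is the least favourable split.

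- Power after the fix: roxadustat rate = 0.80(1 − x).
- Type I error if the rule stays: true rates 80% v 65% under the strict definition, so the roxadustat rate under the present rule is 0.65/(1 − x).

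| x (assumed) | Power after fix, 300/arm | Power after fix, 600/arm | One-sided type I error, rule as written, 300/arm | Same, 600/arm |
|---|---|---|---|---|
| 0 | 99.6% | >99.9% | 2.5% | 2.5% |
| 0.5% | 99.4% | >99.9% | 3.1% | 3.4% |
| 1% | 99.1% | >99.9% | 3.8% | 4.5% |
| 2% | 98.1% | >99.9% | 5.6% | 7.6% |

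If the same x held in both arms, the difference at the margin under the present rule would be −0.15/(1 − x), for example −0.1515 at x = 1%. That is slightly against roxadustat, so there would be no inflation.

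**The case against.** The case for the rule as it stands has real content.

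- **Dating the response at its first value is a natural reading of Protocol 7.1.** It guarantees that the first value is unrescued and looks back about 8 weeks from the second. This stands, but it protects only the first value.
- **The Week 28–36 endpoint is a mean over a period, a different construct.** True, so the comparison is not decisive alone. The 6-week censoring in SAP 11.1.2 still shows that Hb soon after rescue is regarded as rescue-influenced.
- **The ESA route is narrow.** Under Protocol 3.6.3.2, ESA rescue requires an inadequate Hb response, which a subject who has just qualified should not have. This stands. ESA given in hospital remains possible. The protocol does not count it as rescue unless the criteria are met, whereas SAP 4.1 names ESA without that limit; the two texts need reconciling.
- **Other steps will catch some cases.** A low central Hb between the two values breaks the pair. The per-protocol exclusion for prohibited medication (SAP 5.2.5, item 4) might remove some subjects, but it depends on the Medical Monitor's decision, and transfusion is permitted rescue. The US first secondary endpoint is not analysed on the PPS.

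Three stronger readings are tempting, and the documents do not support them.

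- **That a repeat 1 or 2 days later can confirm a response.** The derivation sentence does not restate the spacing and admits unscheduled values. But it requires the criteria of the primary endpoint, which include the 5-day spacing in the same section.
- **That the gap systematically favours roxadustat.** Only the ESA route is one-sided. Transfusion counts in both arms and its effect partly cancels.
- **That a percentage misclassified can be calculated.** Under uniform timing, one 14-day gap covers 14/168 = 8.3% of the 24 weeks, and 22 days covers 13.1%. There is no rescue rate to multiply these by. The second value must also owe its qualification to the rescue, and a later clean pair may restore the subject.

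**Conclusion.** The concern holds on the text. SAP 4.1 leaves the interval between the two qualifying values unchecked, nothing else closes it for this endpoint, and a subject whose confirming value follows rescue can be scored as a responder without rescue.

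The number affected cannot be derived from the documents and is probably small. The type I error figures assume x and place every case in the roxadustat arm. They are a worst-case illustration, not an estimate, and the per-protocol set will be smaller than the randomized numbers used. The reason to act is that the rule decides a regulatory primary endpoint, the planned sensitivity analysis cannot expose the cases, and the correction is simple.

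**What to change.** In the SAP 4.1 derivation, require no rescue therapy from 6 weeks before the first through the date of the second of the two qualifying Hb measurements. Let SAP 4.3, 11.1.1, 11.1.2, 11.2.1.1 and 11.3.1.1 refer to that definition and not restate it. For clarity only, repeat in the derivation sentence the 5-day minimum spacing already in SAP 4.1.

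The cost is one sentence and one programming condition. A few subjects may become non-responders or have a later response date. On the least favourable split above, power at 300 per arm stays at 99.1% if 1% of roxadustat responders are lost and 98.1% if 2% are.

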#### 3.6.3.2 Erythropoiesis Stimulating Agents (Roxadustat Arm Only):

The use of ESAs is not permitted during the Treatment Period, except if all of the following criteria are met:

- A subject's Hb level has not responded adequately despite two or more consecutive roxadustat dose increases or the roxadustat dose has reached the maximum dose limit
- Other causes for lack of response or declining Hb, such as iron deficiency, bleeding, acute inflammatory conditions, have been ruled out
- Reducing risk of alloimmunization in transplant eligible patients is a goal.

Roxadustat and ESA may not be co-administered. Treatment with an approved ESA may be initiated  $\geq$  3 days after the last roxadustat dose.

If the situation permits, the Investigator should inform the Medical Monitor prior to initiation of ESA therapy.

Subjects may receive **one course** of ESA rescue during the Treatment Period.

Erythropoiesis-stimulating agent rescue should stop after 4 weeks or once Hb exceeds 9 g/dL, whichever occurs first. If a subject requires more than 4 weeks of ESA rescue therapy due to inadequate Hb response, the Medical Monitor should be contacted.

Treatment with roxadustat may resume after the following intervals:

- Two days after stopping epoetin alfa
- One week after stopping darbepoetin alfa
- Two weeks after stopping methoxy polyethylene glycol-epoetin beta (Mircera®)

If more than one course of ESA rescue is required during the Treatment Period, the subject must be discontinued permanently from the study, and is considered a Treatment Failure.

Inadvertent ESA administration including ESA administration by hospital staff in Roxadustat subjects should not be counted as rescue unless above criteria are met; these subjects may be allowed to continue on study, if considered safe by the Investigator and Medical Monitor.

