4.4 ADDITIONAL EVALUATION OF EFFICACY

The additional efficacy evaluations in this study are:

- **Hb Correction and Maintenance:**
 - Hemoglobin maintenance: Mean change from baseline in Hb averaged over 8 weeks of treatment at Weeks 28 to 36, without rescue therapy within 6 weeks prior to and during this 8-week evaluation period.
 - Hemoglobin long-term Maintenance: Mean change in Hb averaged over 8 weeks of treatment at Weeks 44-52 without rescue therapy within 6 weeks prior to and during this 8-week evaluation period.
 - Mean change from baseline in Hb averaged over the 96 to 104 weeks of treatment, without rescue therapy within 6 weeks prior to and during this 8-week evaluation period.
 - Change from baseline in Hb at each of the selected post-dosing time points.
 - Proportion of subjects with Hb ≥ 10 g/dL averaged over Weeks 28-36, without rescue therapy within 6 weeks prior to and during this 8-week evaluation period.
 - Proportion of subjects with mean Hb < 9 g/dL, 9- <10 , 10- <11 , 11- <12 , 12- <13 , ≥ 13 g/dL during Weeks 28-36
 - Proportion of patient exposure (PEY) with Hb < 9 g/dL, 9- <10 , 10- <11 , 11- <12 , 12- <13 , ≥ 13 g/dL during weeks 28 to 52
- **Hospitalizations:**
 - Time to first hospitalization (% of subjects) up to Week 52.
 - Time to first hospitalization or skilled nursing facility (% of subjects) up to Week 52
 - Number of days of hospitalizations per patient-exposure year (PEY).
 - Number of days of hospital or skilled nursing facility per PEY
 - Number of medical-facility free days (hospital, skilled nursing facility, emergency room, or overnight observation) per PEY
 - Number of days on treatment out of hospital and skilled nursing facility up to Week 52, 7 days after Last Dose.
- **Missed dialysis sessions up to Week 52**
 - Occurrence (number) of missed dialysis sessions
 - Proportion of subjects with missed dialysis sessions
 - Number of days of missed dialysis sessions per patient-exposure year (PEY)

- **Rescue Therapy Use up to Week 52:**
 - Proportion of subjects who receive RBC transfusions.
 - Number of RBC packs per patient-month exposure to study medication.
 - Roxadustat subjects: The proportion of subjects requiring ESA rescue therapy (ATC code: B03XA01)
- **Changes in Cholesterol Levels:**
 - Change at each of the protocol specified treatment time points in:
 - total cholesterol,
 - low-density lipoprotein (LDL)/high-density lipoprotein (HDL) ratio,
 - non-HDL cholesterol.

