11.3.4.2 ESA Usage as Rescue Therapy for roxadustat-treated Subjects

For roxadustat-treated subjects, ESA, as rescue therapy will be recorded in the ESA log of the eCRF. The total number of ESA-week dose per subject will be calculated.

For each entry that meets the criteria below the ESA-week will be calculated as follows:

- If drug is epoetin alfa, epoetin beta, or an epoetin biosimilar (ATC code: B03XA01), then $\text{ESA-Weeks} = (\text{stop date} - \text{start date} + 1) / 7$;
- If drug is darbepoetin SQ or IV dose (ATC code: B03XA02), then $\text{ESA-Weeks} = 2 \times (\text{stop date} - \text{start date} + 1) / 7$;
- If drug is Mircera IV or SQ dose (ATC code: B03XA03), then $\text{ESA-Weeks} = 4 \times (\text{stop date} - \text{start date} + 1) / 7$;
- If drug is peginesatide dose IV or SQ (ATC cod: B03XA04), then $\text{ESA-Weeks} = 4 \times (\text{stop date} - \text{start date} + 1) / 7$.

The total number of ESA-week during the treatment period is calculated for each subject by the sum of the ESA-week between the analysis date of First dose and the analysis date of Last dose.

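### SAP 4.4 counts ESA rescue by ATC code B03XA01 alone, and SAP 4.1 names the same single code, although SAP 11.3.4.2 lists four ESA codes

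*SAP*

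**What the plan says.** Rescue in the roxadustat arm is defined broadly in SAP 4.1: "Rescue therapy for roxadustat treated subjects is defined as recombinant erythropoietin or analogue (ESA) or RBC transfusion". In the epoetin alfa arm only RBC transfusion counts. The same section then explains how ESA use is captured: it is recorded in the eCRF and "coded into ATC (Code: B03XA01) and generic name".

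SAP 4.4, under rescue therapy use up to Week 52, lists this endpoint: "The proportion of subjects requiring ESA rescue therapy (ATC code: B03XA01)". No generic name is mentioned there.

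SAP 11.3.4.2 deals specifically with ESA as rescue in roxadustat subjects. It takes the data from the eCRF ESA log and shows what each code covers:
- "If drug is epoetin alfa, epoetin beta, or an epoetin biosimilar (ATC code: B03XA01)"
- "If drug is darbepoetin SQ or IV dose (ATC code: B03XA02)"
- "If drug is Mircera IV or SQ dose (ATC code: B03XA03)"
- peginesatide, under B03XA04.

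Protocol 3.6.3.2 permits rescue with an approved ESA, without restricting it to epoetin. It sets intervals for resuming roxadustat after epoetin alfa, after darbepoetin ("One week after stopping darbepoetin alfa") and after methoxy polyethylene glycol-epoetin beta.

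**The concern.** The single code named in SAP 4.1 and 4.4 cannot pick up two of the three rescue drugs for which the protocol makes explicit provision. In SAP 4.4 the code is part of the endpoint definition, so the reported ESA-rescue proportion would be too low.

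More would be at stake if the code were carried into the rescue flag generally. In the ex-US primary and US first secondary responder endpoints, rescue in the 6 weeks before the first qualifying Hb value disqualifies the response. A missed darbepoetin course would let an ESA-supported Hb rise count as a roxadustat response. In the rescue-censored Hb analyses, values supported by the missed ESA would stay in. ESA counts as rescue only in the roxadustat arm, so the epoetin alfa arm has no matching error. The study is open-label, which is a further reason not to leave the rescue flag open to interpretation.

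**Working it through.** **1. Code coverage, using only the documents.**

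| Drug | Code in SAP 11.3.4.2 | Restart interval in protocol 3.6.3.2 | Matched by B03XA01 |
|---|---|---|---|
| Epoetins | B03XA01 | Yes (epoetin alfa) | Yes |
| Darbepoetin | B03XA02 | Yes | No |
| Methoxy polyethylene glycol-epoetin beta | B03XA03 | Yes | No |
| Peginesatide | B03XA04 | No | No |

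**2. Effect on the SAP 4.4 proportion.** Let N be the roxadustat subjects analysed, R those with any ESA rescue, and L those whose rescue used only drugs outside B03XA01. The intended proportion is R/N. The code as written gives (R − L)/N. The shortfall is L/N. It is never negative, and it is zero only if every rescued subject received an epoetin. Neither R nor L is given in the documents.

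**3. Where else rescue status is used.**
- Responder endpoints (SAP 4.1, 4.3): rescue follows the broad definition in 4.1. The sentence with the code describes data coding, adds generic name, and states no filter.
- Rescue-censored MI ANCOVA (SAP 11.1.2 and Table 4): Hb is set to missing for rescue medication, and no code is cited.
- US primary analysis (SAP 4.1, 11.1.2): rescue is not censored, so the code is irrelevant.

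**4. The plan's own figures.** Inputs from SAP 5.1 and section 3: at least 600 subjects, 1:1, so n = 300 per arm; 80% responders in each arm; margin 15 points; two-sided 95% CI.

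Power = Φ{[0.15 − (pC − pT)] / √[pC(1 − pC)/n + pT(1 − pT)/n] − 1.96}

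With pC = pT = 0.80: standard error √(0.32/300) = 0.03266; 0.15/0.03266 − 1.96 = 2.63; power 99.58%. The stated figure of at least 99% reproduces. For the US endpoint (difference −0.30, margin −0.75, SD 1.25 g/dL) the same approach gives 99.28%, also as stated. Neither figure depends on the ESA code.

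**5. What the misreading would do to the ex-US test, by assumption only.** Let f be the share of the roxadustat arm wrongly counted as responders because a non-epoetin ESA was missed. The documents give no value for f, and zero is possible. Corrected power puts pT = 0.80 − f into the formula above. For the one-sided error, the true rates are 0.80 and 0.65 (a difference of exactly −15 points), but the analysis sees pT = 0.65 + f.

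| Assumed f | Subjects of 300 | Power once corrected | One-sided error if uncorrected |
|---|---|---|---|
| 0 | 0 | 99.6% | 2.5% |
| 0.5% | 1.5 | 99.3% | 3.4% |
| 1% | 3 | 98.9% | 4.6% |
| 2% | 6 | 97.4% | 8.1% |

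Example for f = 1%: (0.15 − 0.14)/√[(0.16 + 0.2244)/300] − 1.96 = 0.279 − 1.96 = −1.68, giving 4.6%. These are normal approximations at the minimum sample size, before exclusions from the per protocol set.

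**The case against.** The strongest reply is that the SAP already gets the responder endpoint right. Its definition takes in any recombinant erythropoietin or analogue, so a darbepoetin course is rescue. The coding sentence adds generic name, which would identify the longer-acting drugs whatever their code. The dedicated section, 11.3.4.2, has the full list. A programmer who ignored darbepoetin would be breaking SAP 4.1. This stands, and it rules out saying that the SAP prescribes the misclassification for the responder endpoints or the rescue-censored analyses. It does not fully settle the matter: the 4.1 sentence supplies no list of names and can be read as requiring both the code and the name, and the list in 11.3.4.2 is used to compute ESA-weeks and is not linked to the responder flag.

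A reader might also infer that the responder difference could be inflated by several points, say 5, which would be a third of the 15-point margin. The documents do not support any such figure. A wrongly counted responder must receive a non-epoetin ESA, then meet the Hb criterion at two consecutive visits in the first 24 weeks, with the first value within 6 weeks of that ESA. Protocol 3.6.3.2 makes this group narrow. Rescue requires inadequate response after two or more consecutive dose increases or at the maximum dose, other causes must be excluded, and reducing alloimmunization risk must be a goal. ESA should stop after 4 weeks or once Hb exceeds 9 g/dL, whereas subjects with baseline above 8.0 g/dL need 11.0 g/dL to respond. Inadvertent ESA is not rescue unless those criteria are met.

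Two further limits stand. The SAP 4.4 proportion is an additional evaluation outside the fixed testing sequence. The sensitivity definition in SAP 4.2.1 ignores rescue and so cannot be affected by coding.

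None of this rescues SAP 4.4, where the lone code qualifies the endpoint.

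**Conclusion.** The inconsistency is real, and for the SAP 4.4 ESA-rescue proportion the rule is wrong as written: it omits every subject rescued only with a non-epoetin ESA. The shortfall is L/N, which the documents do not allow one to compute.

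For the ex-US primary and US first secondary responder endpoints, and for the rescue-censored Hb analyses, there is an ambiguity and not a prescribed error. Harm arises only if B03XA01 is used as the filter, contrary to the definition in SAP 4.1. In that case the responder error would run in roxadustat's favour, and so would the Hb analyses to the extent that the missed ESA raised the retained values. The error rates shown above depend entirely on an assumed f and on that reading. No stated power or sample size figure is wrong, and the US primary analysis is unaffected. The change should still be made, since it corrects one summary and closes off a one-sided misreading at almost no cost.

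**What to change.** In SAP 4.1 and 4.4, replace B03XA01 with B03XA01, B03XA02, B03XA03 and B03XA04 plus generic name, taken from the eCRF ESA log, as already listed in SAP 11.3.4.2. Make clear in 4.1 that a match on any listed code or on generic name is enough. Then refer to that single definition for every analysis that uses rescue: the responder endpoints, time to first response, the ex-US Week 28 to 36 Hb endpoint, the rescue-censored MI ANCOVA and the rescue summaries.

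The cost is a wording change and about one line of programming. No new data, visits or sample size are needed, and nothing changes in how subjects are treated.
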